#### **Scoring instructions:**

Convert each original item response code to an item-level raw score, by matching the responses in Appendix B 1. A daily RS-Total score is derived by summing across all 11 item-level scores. Subscale scores are computed as sum of item-level scores for each subscale (domain):

- RS-Breathlessness score will be calculated as the sum of items 7, 8, 9, 10, 11.
- RS-Cough & Sputum score will be calculated as the sum of items 2, 3, 4.
- RS-Chest symptoms score will be calculated as the sum of items 1, 5, 6.

Domain and total scores will not be calculated if at least one item response is missing.

The 4-weekly mean will be calculated as the sum of all non-missing daily scores over the 28day evaluation period, as described in Table 18, divided by the number of non-missing daily scores. The 4-weekly mean will be calculated if there are at least 14 completed days during the 28-day evaluation period, where a day = evening + following morning.

### 3.4.2 Cough Visual Analogue Scale

Change from baseline to Week 12 in average Cough VAS score over the previous 4 weeks is a secondary endpoint of this study.

Participants will be asked to complete a cough severity VAS (100 mm linear scale marked with a horizontal line by the participant, with 0 mm representing "no cough" and 100 mm representing "worst cough") measuring subjective assessment by the participant of the prior 24 hrs for severity of cough symptoms (Smith et al 2006). The cough VAS will be completed each evening in the eDiary.

The 4-weekly mean cough VAS score will be calculated as the sum of all non-missing daily scores over the 28-day evaluation period, as described in Table 18, divided by the number of non-missing daily scores. The 4-weekly mean will be calculated if there are at least 14 completed days during the 28-day evaluation period, where a day = evening + following morning.

## **3.4.3** Breathlessness, Cough and Sputum Scale

Change from baseline to Week 12 in the average BCSS score over the previous 4 weeks is a secondary endpoint of this study.

The BCSS© is a 3-item daily diary that assesses the severity of the 3 symptoms: breathlessness, sputum, and cough, each on a 5-point scale (see Appendix B 4). Item scores will be reported as domains scores and are summed to yield a total score. Higher scores for each domain, and thus for total score, indicate more severe symptoms. The BCSS will be captured each evening via the eDiary.

The 4-weekly mean BCSS score will be calculated as the sum of all non-missing daily scores over the 28-day evaluation period, as described in Table 18, divided by the number of non-missing daily scores. The 4-weekly mean will be calculated if there are at least 14 completed days during the 28-day evaluation period, where a day = evening + following morning.

## 3.4.4 St George's Respiratory Questionnaire

The SGRQ is a 50-item PRO instrument developed to measure the health status of patients with airway obstruction diseases (Jones et al 1991). The SGRQ yields a total score and three domain scores (symptoms, activity, and impacts). The total score indicates the impact of disease on overall health status. This total score is expressed as a percentage of overall impairment, in which 100 represents the worst possible health status and 0 indicates the best possible health status. Likewise, the domain scores range from 0 to 100, with higher scores indicative of greater impairment. Specific details on the scoring algorithms are provided by the developer in a user manual (Jones and Forde 2009). The principle of calculation of total score and domain scores in accordance with the abovementioned user manual are provided in Appendix B 3.

The SGRQ will be completed using the eDiary in accordance with the SoA (CSP Section 1.3), and a 4-week recall version will be used.

The key outcome variable for the SGRQ will be the change in total SGRQ score from baseline to Week 12, but the change in total score from baseline to Week 4 and Week 28 will also be derived (see Section 3.1.3). Change in the domain score from baseline to Week 4, Week 12 and Week 28 will also be derived.

Other variables based on SGRQ to report include:

- Proportion of participants with a decrease in SGRQ score of ≥ 4 points from baseline to Week 12 (Yes=1/No=0)
  - Yes: change from baseline SGRQ score to SGRQ score at Week  $12: \le -4$
  - No: change from baseline SGRQ score to SGRQ score at Week 12: > -4
- Proportion of participants with a decrease in SGRQ score of ≥ 4 points from baseline to Week 28 (Yes=1/No=0)
  - Yes: change from baseline SGRQ score to SGRQ score at Week  $28: \le -4$
  - No: change from baseline SGRQ score to SGRQ score at Week 28: > -4

Participants with missing or non-evaluable SGRQ score will be considered as not achieving SGRQ response.

#### CCI

## 3.4.7 COPD Assessment Test

Participants will be asked to complete a CAT at SV1. The CAT is designed to measure the impact of COPD on a person's life (Jones et al 2009). The CAT consists of eight questions that ask the participant to rate items relating to symptoms and impact on quality of life (such as normal activity and sleep). Each question is performed on a scale from 0 to 5 with 0 being the best possible health status or least impairment and 5 being the worst health status or greatest impairment.

The CAT total score is calculated by summing the scores from each question. The CAT total score has a range from 0 to 40, with higher score denoting a more severe COPD impact on participant's life. A score will not be calculated if at least one response is missing.

## **3.5** Pharmacokinetic variables

Serum samples will be collected for measurement of serum concentrations of MEDI3506 as specified in the SoA in CSP Section 1.3.

## **3.6** Immunogenicity variables

Blood samples for determination of ADA in serum will be assayed by bioanalytical test sites operated by, or on behalf of, AstraZeneca, using an appropriately validated bioanalytical method. Tiered analyses will be performed to include screening, confirmatory, and titer assay components.

### **3.6.1 ADA definitions**

#### ADA detection at participant level:

- A participant is considered ADA positive if a collected sample is tested positive at any time during the study, including baseline and/or post-baseline (see definition for ADA prevalence below).
- A participant is considered ADA negative if collected samples are tested negative at all timepoints, including baseline and post-baseline.

The proportion of ADA-positive participants in a population is known as ADA prevalence.

#### Treatment-related ADA development at participant level:

Treatment-emergent ADA positive (TE-ADA+) is defined as the sum of:

- Treatment-induced ADA positive (ADA negative at baseline and post-baseline ADA positive) and
- Treatment-boosted ADA positive (ADA positive at baseline and boosted (≥4 fold) the pre-existing titre during the study period).

Non-Treatment-emergent ADA positive (non-TE-ADA+) is defined as ADA positive but not fulfilling the definition of TE-ADA positive.

ADA incidence is the proportion of TE-ADA+ participants in a population.

ADA persistently positive is defined as ADA negative at baseline and positive at  $\geq 2$  postbaseline assessments (with  $\geq 16$  weeks between first and last positive) or ADA positive at last post-baseline assessment. ADA transiently positive is defined as ADA negative at baseline and at least one post- baseline ADA positive measurement and not fulfilling the conditions for persistently positive.

The median of maximum titres is calculated based on the maximum titre for each ADA positive participant within each study intervention group (including both baseline and post-baseline measurements).

# 3.6.2 Categories of ADA responses

Numbers and proportions of:

- Participants who are ADA positive at any time during the study, including baseline and/or post-baseline (also generally referred to as ADA positive).
- Participants who are ADA negative at all assessments, including baseline and postbaseline (also generally referred to as ADA negative).
- Participants who are ADA positive at baseline only.
- Participants who are ADA positive at baseline and at least one post-baseline assessment.
- Participants who are treatment-emergent ADA positive (see definition in Section 3.6.1), reported overall and separately as treatment-induced and treatment-boosted participants.
- Participants who are non treatment-emergent ADA positive (see definition in Section 3.6.1).
- Participants who are persistently ADA positive, which is defined in Section 3.6.1.
- Participants who are transiently ADA positive, defined in Section 3.6.1.
- Participants who are ADA positive with maximum titre > median of maximum titres.

# **3.7** Exposure to study intervention

## **Duration of exposure**

Exposure duration (days) is calculated only for participants in the As-treated population as the total number of days on study drug. Exposure is calculated as (the study drug application last date plus 28 days) minus study drug application first date plus one. If any of the first or last dates are missing or partially missing, then imputed dates will not be used, and study drug exposure is set to missing.

#### Number of doses received

Full dose of study drug is administered in 2 injections. The date and time of the first injection will be recorded in eCRF.

Total number of doses received will be calculated as number of study visits where at least one injection with dose level >0 is administered. The first dose of the intervention period intended to be the SV3 dose and the intended last dose of the intervention period is SV11 dose.

#### **Treatment interruptions**

Study intervention is interrupted when at least one of the following events occur:

- Checkbox with action taken with study intervention = "Drug Interrupted" is ticked on EX eCRF;
- There is no dosing (dose recorded as '0' in eCRF) however visit has been performed;
- There is a dose < 4 ml recorded in eCRF (only one syringe has been administered or the volume of 2 syringes is less than intended);

• There are less than 4 kits dispensed and less than 4 kit numbers recorded in eCRF. Permanent drug withdrawal is not considered an interruption.

## **3.8** Safety outcome variables

The following safety data will be collected:

- AEs, SAEs, AESI;
- Vital signs;
- Clinical chemistry, haematology, and urinalysis;
- ECGs;
- LVEF as measured by echocardiogram;
- NT-proBNP;
- SARS-CoV-2 tests.

### **3.8.1** Adverse events

Adverse events and SAEs on this study will be collected from informed consent throughout the intervention period and including the follow-up period. AEs will be coded with MedDRA version 25.1 or higher.

AE data will be allocated to the study phase (as defined in section 3.1.7) according to their onset date.

AEs will be defined as treatment emergent adverse events (TEAEs) if they have an onset, during the on-treatment phase. AEs with a missing start date will be considered as on-treatment.

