#### Adverse event variables

The following variables will be collected for each AE:

- AE (verbatim)
- The date and time when the AE started and stopp:d
- Severity grade
- Whether the AE is serious or not
- Investigator causality rating against the study intervention (yes or no)
- Action taken with regard to the study intervention
- AE caused participant's withdrawal f om study (yes or no)
- Outcome

In addition, the following variable will be collected for SAEs:

- Date AE met criteria for serious AE
- Date investigator b me awar of serious AE
- AE is serious due to
- Date of hospitalisation
- Date of discharge
- Probable cause of death
- Date of death
- Autopsy performed
- Causality assessment in relation to Study procedure(s)
- Causality assessment to other medication

AstraZeneca

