# Appendix B Adverse Events: Definitions and Procedures for Recording, Evaluating, Follow-up, and Reporting

#### **B** 1 **Definition of Adverse Events**

An AE is the development of any untoward medical occurrence in a participant or clinical study participant administered a medicinal product and which does not necessarily have a causal relationship with this study intervention. An AE can therefore be any unfavourable and unintended sign (eg, an abnormal laboratory finding), symptom (for example nausea, chest pain), or disease temporally associated with the use of a medicinal product, whether or not considered related to the medicinal product.

The term AE is used to include both serious and non-serious AEs and can include a deterioration of a pre-existing medical occurrence. An AE may occur at any time, including run-in or washout periods, even if no study intervention has been administered.

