#### 3.1.7 Study phase windows

For the purpose of the statistical analysis, the assessments will be allocated to the study phase in which they are collected as reported below.

Table 20	Study phase windows
----------	---------------------

Study phase	Phase Window for Analysis (Days)
Pre-treatment	Prior to the first administration of investigational product (day <1 a )
On-treatment	$\geq$ day 1 b to last dose date plus 28 days (included)
Follow-up	> last dose date plus 28 days

a Includes all measurements collected before first dose of IP. If the measurement is collected on day 1 it cannot be determined if it was done before or after the first dose of IP (due to missing time and/or planned time point), then it will be considered as collected after first dose of IP.

b Includes all measurements collected on the day of first dose of IP, at the time of IP intake and after.

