## 4.2.10 Safety data

## 4.2.10.1 Adverse events

All AE summary tables and listings will be created by study intervention group for the Astreated population, unless otherwise specified. AEs occurred during study intervention and follow-up period (both periods are defined in section 3.1.7) will be reported in summary tables. All AEs, including AEs for enrolled but not randomized participants and for participants who were not exposed to treatment, will be listed.

Overview tables will contain number and percentages of participants and number of episodes in following categories:

- Any AEs
- Any AE with toxicity grade 4 or 5
- Any AEs with outcome = death
- Any SAEs (including events with outcome = death)
- Any AEs leading to discontinuation of IP
- Any AEs leading to dose interruption
- Any AEs leading to withdrawal from study
- Any AESI

Number and percentage of participants with at least one AE by SOC term will be produced by study intervention group.

Number and percentage of participants with AE by SOC and PT term will be summarised by study intervention group. Total number of AEs by SOC and PT term will be summarised by study intervention group.

The number and percentages of participants with AEs occurring in >5% of participants in Total study intervention group will be summarised by PT and study intervention group. Non-serious adverse events occurring in greater than 5% of participants (including number and percentages of participants and number of events) in any study intervention group by SOC and PT term will be summarised by study intervention group.

The number and percentages of participants with AEs by maximum reported toxicity grade by PT term will be summarised by study intervention group.

The number and percentages of participants with AEs by relationship as assessed by investigator will be summarised by PT term and study intervention group.

Number and percentage of participants with AE leading to dose interruption of IP by SOC and PT term will be summarised by study intervention group.

The number and percentages of participants with AEs with outcome of death by SOC and PT term will be summarised by study intervention group. Key participant information for participants experienced AEs with outcome of death will be produced for each study intervention group using following information:

- Study intervention group
- Participant identifier
- Sex
- Age (years)
- Event term as reported by the investigator
- PT term

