- Time from first IP administration to onset of AE (days) as derived in Section 3.1.8.6
- Treatment period
- Time from last IP administration to death (days) as derived in Section 3.1.8.8
- Time from first IP administration to death (days) as derived in Section 3.1.8.9
- Received treatment for AE
- Reasonable possibility AE caused by IP

The number of SAEs by SOC and PT term will be summarised by study intervention group. The number and percentages of participants with SAEs by SOC and PT term will be summarised by study intervention group. Key participant information for participants experienced SAEs will be produced using following information:

- Study intervention group
- Participant identifier
- Sex
- Age (years)
- Event term as reported by the investigator
- PT term
- Time from first IP administration to onset of AE (days) as derived in Section 3.1.8.6

- Time from last IP administration prior to AE start date, calculated for AEs starting after the discontinuation of the IP.
- Time from start of IP administration to becoming serious
- Outcome
- Action taken with IP
- Reasonable AE caused by IP

The number and percentages of participants with AEs leading to discontinuation of investigational product by SOC and PT term will be summarised by study intervention group. Key participant information for participants experienced AEs leading to discontinuation of IP will be produced using following information:

- Study intervention group
- Participant identifier
- Sex
- Age
- AE as reported by the investigator
- PT term
- Time from first IP administration to AE onset
- Time from first IP administration to discontinuation of IP
- Seriousness
- Outcome
- Reasonable possibility AE caused by IP

Number and percentage of participants with AE of special interest by maximum reported toxicity grade will be summarised by study intervention group. A list of PT terms for AEs of special interest will be produced. Number of participants with AE for each medical concept (injection site reaction (ISR), serious hypersensitivity, serious infection, progression of heart failure, gastrointestinal adverse reactions, COVID-19) by maximum reported toxicity grade will be summarised by study intervention group.

Number of subjects with COVID-19 related AEs of special interest by SOC and PT will be summarised by treatment group and for total MEDI3506. Similar table will be repeated for the number of subjects with COVID-19 related serious AEs of special interest.

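### An adverse event kept as one record with a known pre-dose onset stays out of the AE summary tables even if it turns serious, stops study drug or is fatal after dosing

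*SAP*

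**What the plan says.** SAP 3.8.1 has AEs collected from informed consent to the end of follow-up. It sets the phase by one date only: "AE data will be allocated to the study phase (as defined in section 3.1.7) according to their onset date". The treatment-emergent definition follows the same rule: "AEs will be defined as treatment emergent adverse events (TEAEs) if they have an onset, during the on-treatment phase". The one stated exception is for absent dates: "AEs with a missing start date will be considered as on-treatment".

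SAP 3.1.7 (Table 20) gives the phases. Pre-treatment is "Prior to the first administration of investigational product". On-treatment runs from the first dose to 28 days after the last dose, and follow-up is everything later.

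SAP 4.2.10.1 sets the scope of the tables: "AEs occurred during study intervention and follow-up period (both periods are defined in section 3.1.7) will be reported in summary tables". All AEs, whatever their phase, are listed.

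The protocol's AE variables (Section 8.3.2) hold start and stop dates, one severity grade, action taken with study drug and outcome for each AE. For serious AEs (SAEs) they add "Date AE met criteria for serious AE" and the date of death. The SAP uses the seriousness date in the SAE key participant information, as "Time from start of IP administration to becoming serious", but not to assign a phase. Protocol 9.4.3 plans summaries of treatment-emergent AEs and SAEs without defining the term.

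**The concern.** The run-in lasts at least 4 weeks, so some participants may start dosing with an AE still open. What happens to that AE on study drug is safety information from the treatment period. The SAP classes the whole record by the day it began, and no later clause brings it back.

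At stake are the SAE, death, AE of special interest (AESI) and AE-leading-to-discontinuation tables, which readers use to compare the arms on safety. With about 72 participants per arm, one participant is 1/72 = 1.4% of an arm, so a single missing event can be seen. Some AESI categories, such as serious infection and serious hypersensitivity, depend on seriousness itself. In those, the feature that makes the event of interest may arise only after dosing.

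**Working it through.** The plan states no figure to reproduce. The check applies the written rules to example records.

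**1. Phase windows (SAP 3.1.7).** The last scheduled dose is on day 169, and 169 + 28 = 197. With all doses given, pre-treatment is before first dose, on-treatment is first dose to day 197, and follow-up is from day 198.

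**2. Table filter (SAP 4.2.10.1).** An AE enters the summary tables if its phase is on-treatment or follow-up.

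**3. Example records.** The days are illustrative.

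| Record | Phase by the rule | In AE summary tables |
|---|---|---|
| Onset day -10, becomes serious on day 20 | Pre-treatment | No |
| Onset day -10, IP stopped on day 57 | Pre-treatment | No |
| Onset day -10, fatal on day 40 | Pre-treatment | No |
| Onset day -10, grade 2 to 4 on day 20, same record | Pre-treatment | No |
| Same worsening entered as a new AE, onset day 20 | On-treatment | Yes |
| Start date wholly missing | On-treatment | Yes |
| Start day missing, month of first dose, AE not ended before first dose | Imputed to first-dose date: on-treatment | Yes |
| Onset day 197 | On-treatment | Yes |
| Onset day 198 | Follow-up | Yes |

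The first three rows are the gap. Their onset is known and pre-dose, and nothing that happens later changes the phase.

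**4. Comparison with the imputation rule (SAP 3.1.4.1).** Take an AE that began some days before first dose in the same calendar month and was still open at dosing. If the site recorded only month and year, onset is imputed to the first-dose date and the AE is tabulated. If the site recorded the true day, the AE is left out. Inclusion then depends on how complete the start date is and not on what happened on treatment.

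**5. Comparison with the disposition tables.** SAP 4.2.1 and the shells for Tables 14.1.1.1 and 14.1.1.2 count treatment discontinuations and study withdrawals with reasons, among them adverse event and death. They apply no onset filter. A participant in row 2 or 3 can therefore be counted there and be absent from Tables 14.3.5.1 or 14.3.3.1.

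**6. Dates available for a repair.** The date of becoming serious and the date of death are collected (Protocol 8.3.2). Time from first dose to IP discontinuation is already planned (SAP 4.2.10.1). No date of grade change is listed.

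**The case against.** Five arguments limit the point.

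- **Worsening.** A reader might infer that every run-in AE that worsens is lost, and that the SAP contradicts the protocol's AE definition. The documents do not support this. Protocol Appendix B 1 lets an AE include "deterioration of a pre-existing medical occurrence", and Protocol 8.3.5 makes aggravated examination findings reportable unless clearly due to the disease. A site may therefore enter the worsening as a new AE with a post-dose onset, which is tabulated. Neither document requires this, so the route is open but not assured.
- **The time-to-serious column.** It might be read as contradicting the onset rule. It does not: an AE that starts on day 10 and becomes serious on day 15 fills it properly. It shows only that the SAP expects the two dates to differ.
- **Listings only.** It would be too strong to say that these events appear nowhere but in listings, because the disposition tables count the stops and withdrawals.
- **Eligibility.** Pre-dose checks remove many candidates: conditions judged undesirable, reassessed at SV3 (exclusion 3); clinically significant infection within 4 weeks of Day 1 or suspected at dosing (exclusion 13); broad-spectrum antibiotics within 4 weeks (exclusion 30); and a recent COPD exacerbation (inclusion 10). This stands and makes the number small.
- **One record per AE.** That an AE keeps its original onset when it becomes serious is inferred from the list of AE variables. The eCRF guidance is not in the documents. The inference is reasonable for seriousness, action taken and outcome, which are listed as attributes of an AE, and weaker for worsening.

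The shells' instruction to state the reporting period in a footnote leaves little room, because the text of SAP 4.2.10.1 fixes the scope.

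**Conclusion.** The gap is real for three kinds of event: an AE held as one record, with a known pre-dose onset, that on or after first dose first becomes serious, leads to IP discontinuation, or is fatal. These are missing from the AE, SAE, AESI, death and discontinuation summary tables. They are not missing from the study report.

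The size cannot be computed, because the documents give no rate of AEs open at first dose and no rate at which such AEs progress. Assumed rates could be multiplied out. With 10% to 25% of 144 having an open AE (14 to 36 participants) and 5% to 15% of those progressing, the result is 0.7 to 5.4 participants over both arms. Neither rate has a source, the second also includes grade worsening, and the eligibility checks are ignored. Zero to a few is as much as can be said.

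The rule is the same in both arms, and nothing in the documents shows a bias between them. The primary endpoint is untouched. The conclusion rests on the wording of SAP 3.1.7, 3.8.1 and 4.2.10.1 and on the one-record assumption.

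**What to change.** In SAP 3.8.1, keep the onset rule and add a clause. An AE with pre-dose onset also counts as treatment-emergent if, on or after first dose, it first meets a seriousness criterion (using the seriousness date already collected), leads to permanent discontinuation of IP, or has a fatal outcome. Allocate it to the phase of that later date, so that SAP 4.2.10.1 tabulates it without further change.

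For a grade increase alone, use one route only: eCRF guidance that a post-dose worsening of a pre-dose AE is entered as a new AE with its own start date. Do not also reclassify the original record. No date of grade change is listed, and doing both would count the event twice in the event-count tables (14.3.2.2 and 14.3.2.5).

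The cost is SAP wording, some programming and a line of eCRF guidance. The downside is that a few AEs that began in the run-in move into the tables.
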